4.3 SUB-POPULATION

Patients discharged home with supplemental oxygen will not be randomized and will not be included in the main analyses. However, a separate analysis of these patients will be conducted (section 7.2.2).

4.4 STRATEGIES FOR RECRUITMENT AND RETENTION

Research coordinators will identify eligible patients. Families will be approached by a research coordinator for consent and enrollment, within 2 days of anticipated discharge. Families will receive a \$25 gift card for enrollment and a \$325gift card for study completion. These incentives will also be provided to families of children who are enrolled and then discharged home with supplemental oxygen.

5 PARTICIPANT DISCONTINUATION/WITHDRAWAL

5.1 PARTICIPANT DISCONTINUATION/WITHDRAWAL FROM THE STUDY

Participants are free to withdraw from participation in the study at any time upon request. The investigator may also choose to discontinue or withdraw a participant from the study. The reason for participant discontinuation or withdrawal from the study will be recorded in the research chart.

5.2 LOSS TO FOLLOW-UP

A participant will be considered lost to follow-up if the study staff are unable to contact the parent or legal guardian for the follow-up phone calls. In an effort to decrease loss to follow up, study coordinators will ask parents at enrollment the best days and times of the week to reach them for follow up phone calls. Parents will be provided with the phone number from which they should expect research coordinator phone calls. Where possible, three messages will be left before considering the participant lost to follow-up. The coordinator will document the failed attempts to contact the parent in the research chart.

6 STUDY ASSESSMENTS AND PROCEDURES

6.1 STUDY INTERVENTION

Scheduled follow up

At the time of hospital discharge, parents will be instructed to have their child follow up with their PCP within 4 days of discharge regardless of improvement and/or symptom resolution. Research coordinators will verify that the child has a scheduled follow up appointment prior to discharge and will help with scheduling if necessary.

As needed follow up

At the time of hospital discharge, parents will be instructed that the child does not need to automatically follow up with his/her primary care physician. Rather, the child should follow up on an as needed basis: if the child does not improve or if new concerns arise.

6.2 STUDY PROCEDURES

Consent, screening and study enrollment will occur while the participant is hospitalized for bronchiolitis. Eligibility confirmation will be obtained from the electronic medical record along with parent interview as applicable. Prior to randomizing the eligible patient, the child's parent will be asked to complete the anxiety portion of the HADS, administered verbally by research coordinators. When a RedCap enrollment checklist has been completed, RedCap will supply the local research coordinator with the patient's randomization assignment. The parents will be notified of their randomization group and instructed on the study plan for follow-up as discussed in section 6.1. Patients discharged home with supplemental oxygen will not be randomized, with follow up plans determined by the child's medical team.

Prior to hospital discharge, a research coordinator will call the child's PCP to notify them of the child's enrollment in the trial and their randomization assignment. The research coordinator will fax a one page summary of the trial to the PCP. PCPs will be notified at the time of the call and in the one-page summary that the protocol allows for and encourages PCPs to check-in over the phone with families enrolled in the trial.

Demographic and hospitalization details will be obtained via electronic medical record review. Data for the primary endpoint will be collected by administering the anxiety portion of the HADS survey prior to randomization and at the first post discharge follow-up phone call (5-9 days after discharge). Data for the secondary endpoints will be collected via phone calls from a research coordinator and will occur weekly until symptom resolution or 50 days after discharge, whichever comes first. Research

coordinators will follow a script for all data collection phone calls. Electronic medical record review will supplement information collected by phone calls for patients who re-visit the emergency department or are re-admitted to the hospital. In addition, a one month post discharge phone call will be made to administer the Patient-Doctor Depth-of-Relationship Scale questionnaire. Study participation will conclude with the final discharge phone follow up call.

Table 1: Schema of study procedures

Screening/Enrollment Within 2 days of anticipated hospital discharge

- •Screen potential participants by inclusion and exclusion criteria
- •Obtain informed consent and enroll
- •Obtain demographics and relevant medical history
- •After consent and eligibility verification, but before randomization, parent or legal guardian will complete anxiety portion of HADS

Randomization Day of discharge (patients discharged on oxygen will not be randomized)

- •Coordinator will obtain patient randomization assignment
- •Coordinator will notify child's PCP of child's enrollment in study and randomization assignment
- •Scheduled follow up: Family instructed to follow-up with PCP (appointment made prior to discharge)
- •As needed follow up: Family will be instructed to follow-up with PCP on as needed basis

7 day phone call F	Follow-up assessments of study endpoints
--------------------	--

• Parent will complete anxiety portion of the Hospital Anxiety and Deptression Scale (HADS)

• Parent assessment for secondary outcomes collected via phone interview (see script)

Subsequent weekly phone calls Follow-up assessment of study endpoints

• Parent will be contacted weekly to collect secondary endpoint data until symptom resolution or 50 days after discharge whichever comes first (see script)

1 month follow-up

Follow-up Telephone Call

• Patient-Doctor Depth-of-Relationship Scale will be administered

• Participant considered off study at this timepoint or when final weekly phone call occurs (if needed beyond 4 weeks)

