2.2 SECONDARY OBJECTIVES AND ENDPOINTS

Secondary objectives of the study include determining whether as needed PCP follow-up, compared to scheduled PCP follow-up:

- Does not adversely impact satisfaction with care?
- Does not adversely impact the relationship between the child's primary caregiver and the child's PCP?
- Does not prolong time to resolution of symptoms?
- Does not increase risk of hospital re-admissions and emergency department visits?
- Results in a fewer number of post-discharge ambulatory visits?
- Results in less ambulatory testing (pulse oximetry, chest x-ray) and fewer prescriptions (albuterol, antibiotics, steroids)?
- Results in fewer missed days from daycare and work?
- Results in lower medical costs?

Secondary Outcomes

Measured by parent report via weekly research coordinator phone calls, until symptoms resolved or 50 days after discharge, whichever occurs first:

- Time from hospital discharge to cough resolution
- Time from hospital discharge to child reported back to normal

Measured by parent report via weekly research coordinator phone calls, until symptoms resolved or 50 days after discharge, whichever occurs first:

- Number of hospital re-admissions and emergency visits
- Number of ambulatory visits
- Number of missed daycare and work days
- Ambulatory prescriptions (albuterol, antibiotics, steroids)
- Ambulatory testing (i.e. pulse oximetry, chest x-ray)- only measured at first ambulatory visit

Measured by parent report via research coordinator phone call at 1 month from discharge:

- Relationship with PCP measured by the Patient-Doctor Depth-of-Relationship Scale²⁴
- Satisfaction with care, measured by applicable questions from the Patient Satisfaction Questionnaire Short Form (PSQ-18)²⁵
- Immunizations received

Measured among patients cared for at Intermountain clinics and those who have Select Health insurance:

- Total charges for ambulatory medical care from discharge until:
 - 14 days after discharge
 - symptom resolution

Measured at the time of discharge and during the first follow up phone call:

• Perceptions about pulse oximetry monitoring

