7 STATISTICAL METHODS

7.1 SAMPLE SIZE DETERMINATION

A previous bronchiolitis trial of 615 patients¹⁹ found a standard deviation for HADS scores of 4.1 and a serial correlation of the HADS score between an admission and 7-day assessment that exceeded 0.80 ([name], personal communication, October 18, 2017). To provide as conservative assessment of statistical power, we assume that the serial correlation over 7 days will equal or exceed 0.65 in the present study. We designated a non-inferiority margin on the anxiety portion of the HADS of 2 points, the smallest clinically meaningful change. Based on the non-adherence to recommended follow-up encountered in our pilot study,²² we estimated that up to 33% of patients randomized to as needed follow up would still follow up and that 13% of patients randomized to scheduled follow up would not attend follow up appointments. Hence, the non-inferiority margin for the ITT analysis of all randomized patients was adjusted to be $2 \times (1-0.33-0.13) = 1.08$. We also assumed that the follow-up anxiety assessment would be obtained for at least 90% of subjects. Under these assumptions, a total sample size of 294 patients (147 patients in each group) will provide 80% power with 1-sided α =0.025 for the analysis of covariance planned for the primary analysis to demonstrate non-inferiority of as needed follow up if in fact as needed follow up and scheduled follow up lead to equal levels of anxiety. Because children discharged home with supplemental oxygen are not being randomized and are not being analyzed in the main analysis, these patients are not included in the power calculation.

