8.1.5 DATA HANDLING AND RECORD KEEPING

Data collection is the responsibility of the clinical trial staff at the site under the supervision of the Principal Investigator. Aside from electronic medical review, all data will be collected via verbal interview of parents by research coordinators, adhering to a pre-specified script. All of the validated questionnaires will be read aloud to the parent or legal guardian by research coordinators. The anxiety portion of the HADS, for example, will be read aloud both at baseline and phone follow up, to maintain consistency. Research coordinators will record responses in RedCap. The investigator is responsible for ensuring the accuracy, completeness, legibility, and timeliness of the data reported.

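### No record check is provided for re-admissions and ED visits in families who cannot be reached or do not report them, so events in the only acute-harm outcome may be missed

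*Combined protocol and SAP*

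**What the plan says.** Section 2.2 sets an objective for as-needed follow-up that it "Does not increase risk of hospital re-admissions and emergency department visits". The matching outcome is "Number of hospital re-admissions and emergency visits", and its group of outcomes is "Measured by parent report via weekly research coordinator phone calls, until symptoms resolved or 50 days after discharge, whichever occurs first".

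Section 6.2 (Study Procedures) says that "Electronic medical record review will supplement information collected by phone calls for patients who re-visit the emergency department or are re-admitted to the hospital". The same section has demographic and index-stay details taken from the electronic record. Section 8.1.5 confirms that there are only two sources: "Aside from electronic medical review, all data will be collected via verbal interview of parents by research coordinators".

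Under section 5.2 a child is lost when staff are "unable to contact the parent or legal guardian for the follow-up phone calls", and "Where possible, three messages will be left before considering the participant lost to follow-up". No record check follows. Section 7.2.1 handles loss to follow-up for time to symptom resolution, by censoring. For the count outcomes it names Poisson or negative binomial regression and gives no rule for children who are lost. Section 6.3 leaves parents and coordinators unblinded, and section 8.1.4 says there will be no data monitoring board.

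**The concern.** Taken together, sections 2.2, 5.2 and 6.2 describe an outcome that depends on a parent answering the telephone and mentioning the event. The record is a supplement for children who re-visit, and the calls are the only described way of learning who they are. A family that stops answering could have a child back in hospital without the trial recording it, even though the site holds a record for that child and already opens it for other data.

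The trial may be read as showing that dropping the scheduled visit is harmless, and this is the only outcome that captures acute deterioration. The documents describe no separate adverse-event collection. With very few events expected, losing even one matters. A family whose child is back in the emergency department may also be one that misses a call, so loss could be related to the event.

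**Working it through.** **The plan's own figure.** The only sample-size figure is for the anxiety analysis (section 7.1), and it reproduces.
- Residual SD: 4.1 × √(1 − 0.65²) = 3.116.
- With margin 1.08, one-sided α 0.025 and 80% power: 2 × (1.960 + 0.842)² × 3.116² / 1.08² gives 131 per arm.
- Dividing by 0.90 gives 146 per arm, 292 in total, against 294 stated.

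So 294 is sound as a base. It was not chosen for re-visits.

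**Inputs for re-visits.**
- 294 children, 147 per arm (section 7.1).
- Pilot re-visit rate 2% (section 1.2).
- Loss of 10%. This is an assumption: section 7.1 supposes only that "the follow-up anxiety assessment would be obtained for at least 90% of subjects", which concerns one call.
- Excess risk in lost families, and non-reporting by reached families: assumptions, shown as ranges.

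**Expected events.** 294 × 0.02 = 5.88, or 2.94 per arm.

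**Events missed through loss.** Unobserved children: 294 × 0.10 = 29.4. Observed children: 264.6, with 264.6 × 0.02 = 5.29 events seen.

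| Assumed risk in lost children | Events missed | Total events | Share missed |
|---|---|---|---|
| 2% (equal risk) | 29.4 × 0.02 = 0.59 | 5.88 | 10% |
| 4% | 1.18 | 6.47 | 18% |
| 6% | 1.76 | 7.06 | 25% |
| 10% | 2.94 | 8.23 | 36% |

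At equal risk, the chance that at least one event is missed is 1 − 0.98^29.4 = 45%.

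**Adding non-report.** Suppose 10% to 20% of events in reached families also go unreported. The share missed is then 1 − (5.29 × 0.9)/5.88 = 19% at the low end (equal risk, 10% non-report). It is 1 − (5.29 × 0.8)/7.06 = 40% at the high end (6% risk in lost children, 20% non-report).

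**Effect on the comparison.** The count models estimate a rate ratio. If the same fraction of events is captured in each arm, that fraction cancels, and the loss is in events and precision. If lost children were counted as having no events and loss were 5% in one arm and 15% in the other (assumed), a true ratio of 1.00 would appear as 0.95/0.85 = 1.12 or 0.85/0.95 = 0.89.

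**Precision even with full capture.** With 147 per arm, power to detect 2% against 4% is about 17%, and 2% against 6% about 42%.

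**The case against.** The strongest reply is that section 6.2 defines the children whose records are reviewed by the event, not by the parent's report. A site could satisfy it by screening all its records, and the call script is not part of the documents. This stands in part. A reader might infer that review is confined to children already known to have re-visited and that events are certain to be missed. The text does not say so: how re-visitors are found is unspecified. But it describes no other route than the calls, and a site could follow it exactly and still miss events.

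Other stronger readings also fail:
- **The only safety endpoint.** The documents do not use that label. This is one of many secondary outcomes, and section 2.2 has another no-harm objective, that symptom resolution is not prolonged.
- **Up to half the events missed.** Dividing 2.94 by 5.88 gives 50%, but it takes a 10% risk for lost children in the numerator and 2% for everyone in the denominator. On consistent risks the figure is 36%, and the 10% risk is itself an assumption.
- **Ten percent lost for this outcome.** The 90% figure is for the anxiety assessment at 5-9 days. A family that misses it may answer a later call, and later attrition could equally be larger.
- **Missed events always pull the result toward no increase.** Equal under-capture does not move a rate ratio on average.

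It is also fair to say that about six events will not make this comparison decisive under any method. That limits what the fix can achieve, but it is no reason to lose events that are already in the sites' own records.

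**Conclusion.** The point holds as a gap in ascertainment. Re-visits rest on parent report, record review is only a supplement, and nothing provides for families who are unreachable or do not report. The plan should be changed, although the outcome is secondary and the primary analysis is unaffected.

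At a 2% rate and an assumed 10% unobserved, the likely cost runs from 0.6 of 5.9 events (10%) at equal risk to 2.9 of 8.2 (36%) if lost children carry a 10% risk. Only the 2% and the 294 come from the documents. The loss rate, the excess risk and the non-report rate are assumptions. The certain harm is fewer events and less precision. Bias in the rate ratio needs loss or reporting to differ between arms. The unblinded design makes that possible, but the documents give no figure for it.

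**What to change.** Change section 6.2 so that the participating health systems' records are searched for emergency visits and admissions for every randomized child. This should include children lost to the calls, subject to the terms of any withdrawal. Use one fixed window from discharge to day 50 and the same procedure in both arms, and name the systems searched.

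Align the window for this outcome in section 2.2, which now ends at symptom resolution if that comes before day 50. Count an event found by either source, and state in section 7.2.1 that children lost to calls enter the count models with record-based follow-up.

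Add a sensitivity analysis using record-identified events only. The combined count has two sources for retained children and one for lost children; the record-only count treats both alike.

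The cost is 294 record searches by staff who already use these charts, plus a few lines of text. The sample size does not change. The remaining weakness is that visits outside the participating systems still rest on parent report, and the plan should say so.

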6.3 MEASURES TO MINIMIZE BIAS: RANDOMIZATION AND BLINDING

Randomization

After consent and enrollment, a research coordinator at the site will obtain a site-specific computergenerated randomization assignment for each patient. Patients will be randomized with equal (1:1) allocation to either the scheduled PCP follow up group or to the as-needed PCP follow up group, using randomly permuted blocks of random sizes. Randomization sequences will be stratified by site but not by any additional baseline factors. The research coordinator will inform the patient's family, inpatient medical team, and PCP of the patient's assignment.

Blinding

BeneFIT will be an unblinded trial because it will not be feasible to blind parents or research coordinators to intervention assignment, as the reason for any follow-up visit (i.e. routine vs new concern) that occurs needs to be documented. However, investigators responsible for analyses will be blinded to individual patient intervention assignments.

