2 OBJECTIVES AND ENDPOINTS

2.1 PRIMARY OBJECTIVE AND ENDPOINT

The primary objective of the study is to determine whether as needed Primary Care Physician (PCP) follow-up is non-inferior to scheduled PCP follow-up in terms of reduction in parental anxiety.

Primary Outcome

Parental anxiety, as measured by the anxiety portion of the Hospital Anxiety and Depression Scale (HADS),²³ a validated tool used in a previous trial among parents whose children had been hospitalized for bronchiolitis.¹⁹ Parental anxiety will be measured by research coordinators at before hospital discharge (baseline) and at the first data collection phone call (5-9 days following discharge). The same parent will be interviewed for both the baseline and the follow up HADS. If the length of time between baseline HADS and actual discharge exceeds 2 days, the HADS will be repeated, such that each subject has a baseline HADS within 2 days of hospital discharge.

Justification of Primary Outcome

Our primary outcome was selected based on feedback from primary care providers and parents of children hospitalized for bronchiolitis. Among parents surveyed in our pilot study, "reassurance" was most commonly selected (70%) as the most valuable aspect of the follow up visit.²² Parental reassurance was also mentioned repeatedly by primary care providers from Stanford, Intermountain, and elsewhere via informal discussions with the investigators.

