8.1.3 CONFIDENTIALITY AND PRIVACY

The Institutional Review Board (IRB) or regulatory agencies or other Quality Assurance monitors may request to inspect all documents and records pertaining to the trial, including medical records (office, clinic, or hospital). The clinical study sites will permit access to such records.

Study participant's contact information, necessary for phone call data collection, and study participant research data, which is for purposes of statistical analysis and scientific reporting, will be transmitted to and stored at Stanford University via the RedCap data system. The study data entry and study management systems used by clinical sites will be secured and password protected.

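### Documenting visit reasons does not require the coordinator who reads the day 5-9 HADS to know the allocation, so the primary outcome lacks a cheap, partial safeguard against interviewer bias

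*Combined protocol and SAP*

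**What the plan says.** Section 2.1 makes parental HADS anxiety the primary outcome and assigns its collection to coordinators: "Parental anxiety will be measured by research coordinators at before hospital discharge (baseline) and at the first data collection phone call", the latter 5-9 days after discharge. Under Section 8.1.5 the scale "will be read aloud both at baseline and phone follow up, to maintain consistency".

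Coordinators also handle the allocation. Table 1 in Section 6.2 states "Coordinator will obtain patient randomization assignment", and Section 6.3 has the coordinator tell the family, inpatient team and PCP. Under Section 6.1, coordinators check that the scheduled arm has an appointment and help to book it if needed.

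The only explanation for not blinding them is in Section 6.3: "it will not be feasible to blind parents or research coordinators to intervention assignment, as the reason for any follow-up visit", whether routine or for a new concern, must be documented. The same section blinds the investigators who do the analysis.

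Other safeguards are stated. Section 6.2 says that "coordinators will follow a script for all data collection phone calls" and places the baseline HADS before randomization. Section 2.1 requires the same parent at both assessments. For the 7-day call, Table 1 lists the HADS first and the secondary-outcome interview second. The call script is not part of the document.

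**The concern.** Section 6.3 treats parents and coordinators together, but their situations differ. Parents cannot be blinded to what they were told to do. For coordinators, the plan offers only the need to record why a visit took place, and that concerns a secondary-outcome question.

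The primary outcome is subjective and interviewer-read, so tone, prompting or the parent's wish to please can influence answers. An effect common to both arms cancels. One that differs by arm because the caller knows the allocation goes straight into the primary contrast. The baseline HADS precedes randomization, so only the follow-up score is exposed, and adjusting for baseline cannot remove such a difference.

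The intent-to-treat margin is 1.08 points, so even a small differential effect could change the conclusion.

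**Working it through.** **Does the stated reason require an unblinded HADS reader?**

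1. Section 6.3 needs the reason for a visit. The parent can supply it during the call, and the caller need not know the arm beforehand.
2. Table 1 puts the HADS and the secondary-outcome interview in the same 7-day call, HADS first. Nothing in the plan requires visit questions to precede it.
3. Hearing that a visit took place does not fully reveal the arm. Section 7.1 allows for up to 33% of as-needed families attending and 13% of scheduled families not attending.
4. The script, constant verbal mode, same parent, pre-randomization baseline and blinded analysts leave the knowledge of the person administering the follow-up HADS unchanged.

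**How sensitive is the primary test?**

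Inputs from Section 7.1: SD 4.1, correlation 0.65, 90% follow-up, 147 per arm, one-sided alpha 0.025, true difference 0. The margin is 2 × (1 − 0.33 − 0.13) = 1.08.

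The plan's sample size, first:

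- Residual SD = 4.1 × √(1 − 0.65²) = 3.116.
- Normal approximation: n = 2 × [3.116 × (1.960 + 0.842) / 1.08]² = 130.7, so 131 per arm. Then 131 / 0.9 = 145.6, so 146 per arm and 292 in total.
- Using the t distribution: 132 per arm. Then 132 / 0.9 = 146.7, so 147 per arm and 294 in total, as stated.

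With 147 × 0.9 = 132.3 analysed per arm:

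- SE = 3.116 × √(2 / 132.3) = 0.383.
- Largest observed difference that still shows non-inferiority: 1.08 − 1.960 × 0.383 = 0.33 points.
- Power at a true difference of 0: Φ(1.08 / 0.383 − 1.960) = 80.5%.

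Let b be an assumed shift in the as-needed minus scheduled difference. The document gives no value for b.

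- Shift favouring as-needed follow-up, true difference 1.08: false non-inferiority = Φ(b / 0.383 − 1.960).
- Shift against it, true difference 0: power = Φ((1.08 − b) / 0.383 − 1.960).

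| Assumed b (points) | False non-inferiority, shift favouring as-needed | Power, shift against as-needed |
|---|---|---|
| 0 | 2.5% | 80.5% |
| 0.1 | 4.5% | 72.5% |
| 0.25 | 9.6% | 58.2% |
| 0.5 | 25.6% | 32.8% |

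Section 7.1 also reports that the correlation exceeded 0.80 in a previous trial. At exactly 0.80, false non-inferiority for 0.1, 0.25 and 0.5 points is about 5%, 13% and 38%. The smaller standard error makes a given bias matter more.

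**The case against.** The strongest reply is that the trial is openly unblinded and the outcome is the parent's own report, so parents' knowledge of their arm remains whatever the interviewer knows. Scripted reading in a constant mode also limits tone and prompting. Both points stand. They limit the gain from concealment but do not explain why the reader must know the arm.

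The illustrative shifts have no anchor in the document, and the same formula would describe bias from any source. That also stands. The table shows the test's sensitivity. It does not estimate interviewer bias or the part that concealment would remove.

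Four stronger readings are tempting, and the document supports none of them:

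- **Interviewer bias will push toward non-inferiority.** No mechanism pulling the arms together is described, and the effect could equally cost power.
- **The enrolling coordinator makes the call.** The plan does not say who places it, and booking help is given only when necessary.
- **Visit questions now come before the HADS.** The script is not available, and Table 1 suggests the opposite order.
- **Calls can simply be exchanged between hospitals.** Section 8.1.3 says that "contact information, necessary for phone call data collection" is stored at Stanford, but not that one site's coordinators may call another site's families. Section 8.1.5 gives data collection to site staff, and coordinator numbers are not stated.

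**Conclusion.** The point holds as a gap in protection of the primary endpoint: the reason in Section 6.3 does not justify unblinded reading of the follow-up HADS, and no stated safeguard covers it. Any differential interviewer effect would bias the primary contrast in an unknown direction and by an unknown amount.

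The illustrative figures rest on the plan's SD of 4.1, correlation of 0.65 and 90% follow-up, and on assumed shifts. The sample size of 294 is reproduced and is not in dispute. The change is worth making because it costs little, although only the interviewer's part of the bias can be reduced.

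**What to change.** Amend Sections 6.2 and 6.3 as follows:

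1. The HADS is completed and saved first in the day 5-9 call. Confirm this against the call script; if that is already the order, state it in the protocol.
2. REDCap hides allocation and visit items until the HADS form is saved.
3. Parents are asked at the start of the call not to mention follow-up plans until the scale is finished.
4. The caller records whether the arm was known beforehand or disclosed early.
5. Where an existing coordinator who did not enrol the family is available, that person makes this call. Item order and hidden fields cannot blind a caller who already delivered the assignment.

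The cost is a call roster, REDCap form settings, a line in the script and some scheduling effort. Sample size and analysis are unchanged, and no staff need be added, because step 5 applies only where a second coordinator exists. Protection stays partial: some parents will reveal their arm, and a site with one coordinator may be unable to swap. The record in step 4 will show how often concealment failed.
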